**7.2.6. Statistical Methodology Specification**

Secondary Statistical Analyses
Endpoint

 
• Annualized rate of moderate/severe asthma exacerbations
 

Model Specification

 
• Generalized linear model assuming a negative binomial distribution
 
• The analysis is based on ‘de facto’ type estimand, including all moderate/severe exacerbations observed during the study (both on- and post-treatment).
 
• Terms in the model:             
 
• Dependent variable: number of recorded moderate/severe asthma exacerbations experienced per participant during the study (both on- and post-treatment).
 
• Covariates:
 
 
 

Secondary Statistical Analyses
 
 
○ Categorical: treatment group, sex, region, pre-study ICS dosage at screening, severe asthma exacerbations in the previous year (0, 1, >=2).
 
○ Continuous: age.
 
● Offset: logarithm of time (year) on study
 
● For the pooled analysis: 
 
○ All 6-arm data are included in the model.
 
○ LSMESTIMATE statement will be used with the treatment code as specified Section 7.
 
 
 
● Mean annualized rate of moderate/severe asthma exacerbations will be estimated using the observed marginal distributions of the study population covariates by inclusion of the OM (obsmargins) option.
 

Model Checking & Diagnostics
 
 
● Refer to Appendix 8: Model Checking and Diagnostics for Statistical Analyses.
 

Model Results Presentation
 
 
● Summary table of the number of events, and details of the events will be produced for the periods Weeks 1-24, 1-52 and 25-52 (See Section 11.6.3 for more details)
 
● Treatment group mean annualized moderate/severe exacerbation rates, treatment rate ratios and associated 95% confidence intervals (CI) and p-values will be presented for all treatment comparisons specified in Section 7. The treatment rate ratios and associated 95% CIs will also be presented graphically.
 
● Percentage reduction in annualized moderate/severe exacerbation rates and associated 95% CIs will also be presented.
 


Exploring Interaction Terms
 
 
● Interaction by treatment terms will added to the main model one at a time for the following main effect covariates: age, region, sex and pre-study ICS dosage at screening, severe exacerbations in the previous year.
 
● Summary of test results for main effect covariates in main model will be presented along with the test results for the interaction terms mentioned above.
 

Supportive Statistical Analyses
 
 
● An 'on-treatment' analysis will be performed, corresponding to the 'de jure' type estimand analysis specified in the protocol. 
 
○ The endpoint/variable, summary measure and population of interest will be the same as for the primary analysis, as outlined in Section 7.2.1, Section 7.2.2 and Section 7.2.3 respectively.
 
○ The covariates will be included in the model as stated above.
 
○ Offset: logarithm of time (year) on treatment.
 
○ Strategy for Intercurrent (Post-Randomization) Events: 
 
▪ An "on-treatment" strategy will be used to handle the intercurrent event of treatment discontinuation. Data collected after treatment discontinuation will be excluded from the analysis and only on-treatment data will be used.
 
▪ No imputation of missing data is planned. Missing data is assumed Missing at Random (MAR).
 
 
 
 
 

Sensitivity analysis - removing sites
 
The primary model will be repeated excluding participants from sites PPD and PPD using data from weeks 1-52.
 
The results of the fitted model will be presented. Summaries and figures will not be produced.

Secondary Statistical Analyses
Sensitivity Statistical Analyses – missing data imputation

 
• Generalized linear model assuming a negative binomial distribution
 
• Imputation methods: 
 
• Tipping Point
 
• Jump to Reference
 
 
 
• For each of the multiple imputations, the complete datasets of moderate/severe asthma exacerbations (both recorded and imputed) will then be analysed using a negative binomial model (on each imputation).
 
• Imputation and analysis model: 
 
• Dependent variable: 
 
○ Imputation model: Number of recorded moderate/severe asthma exacerbations experienced per participant.
 
○ Analysis model: Number of recorded and imputed moderate/severe asthma exacerbations experienced per participant.
 
 
 
• Covariates: 
 
○ Categorical: treatment group, sex, region, pre-study ICS dosage at screening, severe asthma exacerbations in the previous year (0, 1, >=2).
 
○ Continuous: age.
 
 
 
• Offset: logarithm of time (year) on study (imputation: on- and post-treatment data, analysis: including imputed time on study up to EOS or planned EOS).
 
 
 
• All 6-arm data are included in the model.
 
• LSMESTIMATE statement will be used with the treatment code as specified Section 7.
 
• Multiple imputation methods will be used with results from the negative binomial model combined across imputations on the log-scale, using Rubin's method [Rubin 1987] as implemented in SAS PROC MIANALYZE before exponentiating to obtain the estimates for the rates and rate ratios
 
• Details for the sensitivity analysis under each imputation method for post-study missing data are provided in Section 7.2.1.
 
• The mean annualized exacerbation rate, rate ratio (and 95% CIs) for the primary comparison of interest detailed in Section 7 will be presented. For the J2R imputation, the percentage reductions (and 95% CIs) will also be presented.
 
• A forest plot of the rate ratios (and 95% CI) will be presented for the de facto, de jure, sensitivity and J2R analyses.
 
• For the tipping point analysis, a heat map of the p-values will be produced for each of the primary comparisons of interest for the different deltas applied. A line plot of the rate ratio and 95% CI will also be produced across the deltas applied to the UMEC/FF/VI arms, with the delta for the FF/VI arm set to 0 (MAR). The tipping point where the two-sided p-value rises above 0.05 will be included in the plot if possible.
 
• Model checking and diagnostics will not be performed for the imputed datasets.
 

Unpooled data
The 'de facto' summary outputs, analysis and figures will be repeated on the unpooled data.
Subgroups
Summaries will be presented for weeks 1-52 for each of the subgroups listed in Section 5.5.2.

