
The deltas to be investigated are pre-selected multiples of the observed treatment effect. If the observed treatment effect from the primary analysis is  $x$ , the deltas to be investigated will range from  $-3x$  to  $+x$  mL for both active and placebo arms, in increments of  $0.5x$  mL. The increment or range may be refined based on the analysis results and the location of the tipping point.

For each of the four primary comparisons of triple vs. dual (a fixed dose of FF and a fixed dose of UMEC): the delta for these two relevant FF/UMEC/VI and FF/VI arms will be allowed to vary independently, while assuming MAR (delta=0mL) for the other four treatment arms. The imputation model will contain the same terms as in the primary analysis MMRM model.

For a given pair of ‘delta comparison’ as in the table below, complete sets of Week 24 data for all 6 treatment arms will be produced with multiple imputation based on missing at random (MAR) assumption. For each of the multiple imputations, the relevant deltas (+ and/or -) will be added to the imputed FEV1 under MAR for each respective treatment arm.

For example, the grid for the comparison between FF/UMEC/VI 100/62.5/25 and FF/VI 100/25 is as follows: The mean change from baseline post-withdrawal from study is calculated as mean of delta + change under the MAR assumptions (FF/UMEC/VI 100/62.5/25 =  $z$  (mL), and FF/VI 100/25 =  $y$  (mL)) for each respective treatment group. Of the less interest for the sensitivity analysis are the greyed-out grid points for the deltas where FF/UMEC/VI performs relatively better than FF/VI.

			FF/UMEC/VI 100/62.5/25								
			Delta (mL)								
			-3x	-2.5x	-2x	-1.5x	-x	-0.5x	0	0.5x	x
FF/VI 100/25	Delta (mL)	Mean change post-withdrawal	-3x+z	-2.5x+z	-2x+z	-1.5x+z	-x+z	-0.5x+z	z	0.5x+z	x+z
	-3x	-3x+y									
	-2.5x	-2.5x+y									
	-2x	-2x+y									
	-1.5x	-1.5x+y									

-x	-x+y									
-0.5x	-0.5x+y									
0	y									
0.5x	0.5x+y									
x	x+y									

The analysis results will be used to evaluate the plausibility of the assumed difference from MAR for missing outcomes on each treatment arm under which (Tipping Point) the conclusions change, i.e., under which there is no longer evidence of a treatment effect, and clinical judgment will be applied as to the plausibility of the associated assumptions.

Repeat this process for each of the four primary treatment comparisons of interest as outlined in Section 7.

2. Jump to Reference:

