The 'de facto' type estimand analysis for the key secondary endpoint includes all moderate/severe asthma exacerbations following discontinuation of randomized treatment for participants who remain in the study and assumes that any remaining missing data due to early withdrawal from study prior to the planned end of study visit is Missing at Random (MAR). To examine the sensitivity of the analysis result to departures from this assumption, further sensitivity analyses will be performed using alternative assumptions analogous to those used for the primary endpoint. For each proposed imputation method, the sensitivity analysis will include both observed (on and post-treatment) and imputed asthma exacerbation events. The following different algorithms are proposed to impute the post-treatment missing data.

These analyses will be performed for weeks 1-52 only.

For each approach, exacerbations in the unobserved period will be imputed only up to the participant's planned end of study visit date determined by participant's randomization date (see Section 11.3.2).

- Tipping Point:

This method will explore the potential effect of missing data on the reliability of the results by using different assumptions regarding the moderate/severe asthma exacerbation rate in participants who withdraw from study early. Participants who withdrew from the study earlier than their planned end of study will have missing data imputed for the period of time between withdrawal from the study to the planned end of study visit first assuming missing at random (MAR) and then multiplying the estimated exacerbation rate under MAR by different deltas. The imputed exacerbation rates will vary independently for FF/UMEC/VI arms and FF/VI arms.

The deltas to be investigated are pre-selected multiples of the observed rate reduction. If the observed rate reduction from the key secondary analysis is  $x$ , the deltas to be investigated will range from  $1-x$  to  $1+3x$  for both active and placebo arms, in increments of  $0.5x$  (For example, if the observed rate reduction is 20% ( $x=0.2$ ) the imputed rates will be multiplied by deltas of 0.8 to 1.6 in increments of 0.1). The increment or range may be refined based on the analysis results and the location of tipping point.

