For the comparison of FF/UMEC/VI UMEC 62.5 vs. FF/VI: a delta is applied to the two triple arms involving UMEC 62.5, and separately a delta is applied to the two FF/VI arms, and both deltas will be allowed to vary independently; the delta will be equal to 1 (i.e., under MAR assumption) for the triples involving UMEC 31.25. The same approach will be taken for the comparison of FF/UMEC/VI UMEC 31.25 vs FF/VI, this time varying the delta applied to the triple arms involving UMEC 31.25 and setting the delta for the triples involving UMEC 62.5 equal to 1. The imputation model will contain the same covariates as in the key secondary endpoint analysis (de facto) model (with MAR rates being delta-adjusted).

For a given pair of ‘delta comparison’ as in the table below, complete sets of exacerbation data (observed and imputed exacerbations) for all 6 treatment arms will be produced with multiple imputation based on missing at random (MAR) assumption. For each of the multiple imputations, the relevant deltas will be multiplied to the imputed exacerbation rates under MAR for the respective treatment arms.

For example, the grid for the comparison between triples at UMEC 62.5 and duals is as follows: The post-withdrawal mean rate is calculated as the delta \*mean rate under the MAR assumption (triples at UMEC 62.5 =  $z$ , and duals =  $y$ ). The greyed-out grid points for the deltas are of less interest in the sensitivity analysis where Triples FF/UMEC/VI at UMEC 62.5 performs relatively better than duals FF/VI when the imputed exacerbations for the post-withdrawal missing data are deviated from the estimates under MAR in the pooled (FF doses) analysis for the respective treatment arms. The cell with delta = 1 for both FF/UMEC/VI and FF/VI represents the key secondary analysis result under MAR.

			Triples at UMEC 62.5				
			Delta				
			0.8	1	1.2	1.4	1.6
Duals	Delta	Mean rate post-withdrawal	$(1-x)*z$	$1*z$	$(1+x)*z$	$(1+2x)*z$	$(1+3x)*z$
	1.6	$(1+3x)*y$					
	1.4	$(1+2x)*y$					
	1.2	$(1+x)*y$					
	1	$1*y$					
	0.8	$(1-x)*y$					

The analysis results will be used to evaluate the plausibility of the assumed difference from MAR for missing outcomes on each treatment arm under which (Tipping Point) the conclusions change, i.e., under which there is no longer evidence of a treatment effect, and clinical judgment will be applied as to the plausibility of the associated assumptions.

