2.24.	ITT	EFF_F6	Tipping Point Line Plot Adjusted Moderate/Severe Asthma Exacerbations Rate Ratio over Weeks 1-52 FF/UMEC/VI UMEC 62.5 vs. FF/VI (On- and Post-Treatment) - Pooled FF Doses	Weeks 1-52	SAC
2.25.	ITT	EFF_F5	Tipping Point Heat Plot for Adjusted Moderate/Severe Asthma Exacerbations Rate Ratio over Weeks 1-52 FF/UMEC/VI UMEC 31.25 vs. FF/VI (On- and Post-Treatment) - Pooled FF Doses	Weeks 1-52	SAC
2.26.	ITT	EFF_F6	Tipping Point Line Plot Adjusted Moderate/Severe Asthma Exacerbations Rate Ratio over Weeks 1-52 FF/UMEC/VI UMEC 31.25 vs. FF/VI (On- and Post-Treatment) - Pooled FF Doses	Weeks 1-52	SAC
2.27.	ITT	EFF_F9	Forest Plot of Adjusted Moderate/Severe Asthma Exacerbations Rate Ratio (On- and Post-Treatment)	Weeks 1-24 and 1-52	SAC [1]
Other Secondary Efficacy Endpoints					
2.28.	ITT	EFF_F1	Box Plot of Change from Baseline in Clinic FEV 1 (L) at 3 Hours Post Study Treatment at Week 24 (On-Treatment)	At week 24	SAC
2.29.	ITT	EFF_F2	Empirical Distribution Function Plot of Change from Baseline in Clinic FEV 1 (L) at 3 Hours Post Study Treatment at Week 24 (On-Treatment)	At week 24	SAC
2.30.	ITT	EFF_F10	Least Squares Mean (95% CI) Change from Baseline in Clinic FEV 1 (L) at 3 Hours Post Study Treatment at Week 24 (On-Treatment)	At week 24	SAC
2.31.	ITT	EFF_F11	Least Squares Mean (95% CI) Treatment Difference in Change	At week 24	SAC

Efficacy: Figures					
No.	Population	IDSL / Example Shell	Title	Programming Notes	Deliverable [Priority]
			from Baseline in Clinic FEV 1 (L) at 3 Hours Post Study Treatment at Week 24 (On-Treatment)		
2.32.	ITT	EFF_F10	Least Squares Mean (95% CI) Change from Baseline in Clinic FEV 1 (L) at 3 Hours Post Study Treatment at Week 24 (On-Treatment) - Pooled FF Doses	At week 24	SAC
2.33.	ITT	EFF_F11	Least Squares Mean (95% CI) Treatment Difference in Change from Baseline in Clinic FEV 1 (L) at 3 Hours Post Study Treatment at Week 24 (On-Treatment) - Pooled FF Doses	At week 24	SAC
2.34.	ITT	EFF_F1	Box Plot of Change from Baseline in SGRQ Total Score (On- and Post-Treatment) - Pooled FF Doses	At weeks 12, 24, 36 and 52	SAC
2.35.	ITT	EFF_F2	Empirical Distribution Function Plot of Change from Baseline in SGRQ Total Score (On- and Post-Treatment) - Pooled FF Doses	At weeks 12, 24, 36 and 52	SAC
2.36.	ITT	EFF_F3	Least Squares Mean (95% CI) Change from Baseline in SGRQ Total Score up to Week 24 (On- and Post-Treatment) - Pooled FF Doses	At weeks 12, and 24	SAC

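### The exacerbation tipping-point line plot (SAP 7.2.6) fixes the FF/VI delta at 0 and labels it MAR, but SAP 7.2.5 defines delta as a multiplier whose MAR value is 1

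*SAP*

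**What the plan says.** In SAP 7.2.5, post-withdrawal exacerbations are imputed by "first assuming missing at random (MAR) and then multiplying the estimated exacerbation rate under MAR by different deltas". With x the observed rate reduction, delta runs from 1-x to 1+3x. The SAP's example takes x = 0.2, giving 0.8 to 1.6 in steps of 0.1, and lets the range be refined once results are seen. The MAR point is stated twice. For the arms outside the UMEC 62.5 comparison, "the delta will be equal to 1 (i.e., under MAR assumption) for the triples involving UMEC 31.25". For the grid itself, "The cell with delta = 1 for both FF/UMEC/VI and FF/VI represents the key secondary analysis result under MAR".

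SAP 7.2.6, in its block on missing-data imputation, asks for a line plot of the rate ratio and its 95% CI "across the deltas applied to the UMEC/FF/VI arms, with the delta for the FF/VI arm set to 0 (MAR"). For the offset, the same block says "analysis: including imputed time on study up to EOS or planned EOS". It also says "Details for the sensitivity analysis under each imputation method for post-study missing data are provided in Section 7.2.1", but 7.2.1 only names the endpoint.

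The displays concerned are in SAP 11.10.7: Figure 2.24, titled "Tipping Point Line Plot Adjusted Moderate/Severe Asthma Exacerbations Rate Ratio over Weeks 1-52 FF/UMEC/VI UMEC 62.5 vs. FF/VI", and Figure 2.26, its counterpart for UMEC 31.25.

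For trough FEV1, SAP 7.1.5 adds delta to the imputed value, varying it in the two arms compared "while assuming MAR (delta=0mL) for the other four treatment arms".

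**The concern.** The same parameter has two different MAR values in adjacent sections. On a multiplicative scale, 0 is the extreme opposite of neutral: it says that FF/VI participants who left the study would have had no further exacerbations.

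The line plot exists to show how pessimistic the assumption about triple-arm withdrawals must be before the key secondary result loses significance. If the control arm is held at zero events and not at MAR, the plot answers a different question and shows the result as more fragile than it is.

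Two features make the slip easier to carry into code. The block sends the programmer to a section that does not define delta. The exacerbation line plots also share example shell EFF_F6 with the FEV1 line plots (Figures 2.11, 2.13, 2.15 and 2.17), where delta is additive and 0 is the MAR value.

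**Working it through.** **Scale check.** At x = 0.2 the rule in 7.2.5 gives a lower limit of 1-0.2 = 0.8, an upper limit of 1+3(0.2) = 1.6 and a step of 0.5(0.2) = 0.1. This reproduces the SAP's example. The grid contains 1 and not 0; since the smallest delta is 1-x, 0 is reached only at x = 1. The post-withdrawal FF/VI rate is delta times the MAR rate y. Delta 1 gives y, which is MAR. Delta 0 gives 0, which is not.

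**Effect if 0 is programmed.** Let f be the unobserved share of planned follow-up time, taken as equal in both groups. The offset counts imputed time, so the FF/VI rate is multiplied by (1-f). With d the triple-arm delta and a true rate ratio of 0.80:

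- FF/VI at 1: RR = 0.80 × (1 + (d-1)f)
- FF/VI at 0: RR = 0.80 × (1 + (d-1)f) / (1-f)

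**Standard error.** The table in protocol 9.2.2 gives power 0.92 for 750 per arm, rate 2.00, 20% reduction and dispersion 0.7. So SE(log RR) = 0.2231/(1.960 + 1.405) = 0.0663. Holding this SE fixed, p = 0.05 is reached at RR = exp(-1.96 × 0.0663) = 0.878.

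**Values of f.** The documents give none. Protocol 9.2.1 assumes 10% missing spirometry at Week 24 due to early withdrawal. From that anchor:

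- A: 10% withdraw evenly over planned follow-up, so f = 10%/2 = 5%.
- B: constant hazard giving 10% by Week 24, so the weekly hazard is -ln(0.9)/24 = 0.00439. The accrual in 9.2.1, with follow-up cut at 24, 36 or 52 weeks, puts 48%, 40% and 12% of subjects in those groups, a mean of 32.2 weeks. Expected observed time is 29.8 weeks, so f = 1 - 29.84/32.17 = 7.2%.

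The values 2% and 10% are added to show the range.

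**Results.** The tipping delta is 1 + (0.878/0.80 - 1)/f with FF/VI at 1, and 1 + ((0.878/0.80)(1-f) - 1)/f with FF/VI at 0.

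| f | RR at d = 1, FF/VI at 0 | p | Tipping d, FF/VI at 1 | Tipping d, FF/VI at 0 |
|---|---|---|---|---|
| 2% | 0.816 | 0.002 | 5.88 | 4.8 |
| 5% (A) | 0.842 | 0.010 | 2.95 | 1.86 |
| 7.2% (B) | 0.862 | 0.025 | 2.36 | 1.26 |
| 10% | 0.889 | 0.076 | 1.98 | 0.88 |

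The two tipping deltas differ by 0.878/0.80 = 1.10 at every f, because f cancels. The whole planned range, 0.8 to 1.6, is only 0.8 wide.

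With FF/VI correctly at 1, the line does not tip by 1.6 at any of these f. With 0, it still does not under A, it tips within the range under B, and at 10% it has already tipped with the triple arms at MAR.

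**Sensitivity to the SE.** Protocol 9.2.1 quotes about 95% power for the scenario that the 9.2.2 table puts at 0.92. Using 0.95, SE = 0.0619 and the tips are 3.14 against 2.04 (A) and 2.49 against 1.38 (B). With the 2,439 participants randomized in SAP 5.4 (813 per pooled group, SE 0.0637) they are 3.07 against 1.96 and 2.43 against 1.33. The pattern is unchanged.

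**The case against.** The best defence is that the plan largely corrects itself. The MAR label stands beside the numeral, and the section just before says twice that MAR is 1. A line plot drawn as one row of the tipping-point grid would have no delta = 0 imputation to use. Someone would have to run an extra imputation contradicting its own label, and the result would visibly disagree with the heat plots. This stands, and it is why the harm is conditional.

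The carry-over route is also unproven. Example shells are kept in separate documents (SAP 11.10.2), and the heat plots share shell EFF_F5 across both endpoints without raising a problem. The misdirected cross-reference is softened by SAP 7.2.4 and 11.7.2.2, which cite 7.2.5 correctly. These points support checking the code, not assuming that it is wrong.

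The size is illustrative. The 10% anchor concerns missing spirometry, not unobserved exacerbation time, and the upper limit of 1.6 is adjustable under 7.2.5. The statements about tipping inside the range therefore depend on a limit that may move.

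None of this makes 0 correct. A log-scale delta would put MAR at 0, but 7.2.5 defines a direct multiplier. The log scale in 7.2.6 concerns combining results across imputations.

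**Conclusion.** The inconsistency is real, and 0 cannot be MAR under the SAP's own definition. It is minor. The intended meaning is clear, and only Figures 2.24 and 2.26 are exposed, and only if the numeral is coded literally. The key secondary test, the testing hierarchy, heat plots 2.23 and 2.25, Tables 2.43 to 2.46 and the jump-to-reference analysis do not depend on it.

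The direction is conservative: the control rate is understated, the rate ratio moves towards 1, and the triple therapy result looks more fragile than it is. The tipping delta would come about 1.1 too early, assuming a true rate ratio of 0.80, the planning standard error held fixed, and the same unobserved share in both groups. Whether that creates a false tip inside the planned range depends on f, which the documents do not supply.

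**What to change.** In SAP 7.2.6, change the FF/VI delta for the line plot from 0 to 1, keeping the MAR label, and point the imputation details to Section 7.2.5 in place of 7.2.1. Then confirm that the shell and code for Figures 2.24 and 2.26 hold FF/VI at 1 and do not inherit 0 from the additive FEV1 plots. A simple test is that each line, at triple-arm delta 1, should match the delta = 1 cell of the corresponding grid.

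The cost is two text corrections and a check of two figures. No other analysis changes.

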### 7.3. Other Secondary Analyses

An overview of the planned secondary analyses is provided below. The full details of secondary efficacy analyses data displays are presented in [Appendix 10: List of Data Displays](#).

Endpoint	Absolute			Change from Baseline				
	Stats Analysis	Summary	Individual	Stats Analysis		Summary		Individual
	T	T	L	T	F	T	F	L
Clinic FEV 1 at 3 hours post study treatment (de jure type estimand)	Y	Y	Y	Y	Y	Y	Y	Y
Clinic FEV 1 at 3 hours post study treatment (de jure type estimand, pooled FF doses)	Y	Y		Y	Y	Y	Y	
SGRQ total score using pooled FF doses (de facto type estimand)	Y	Y		Y	Y	Y	Y	
SGRQ total score (de facto type estimand)	Y	Y		Y	Y	Y	Y	
ACQ-7 total score using pooled FF doses (de facto type estimand)	Y	Y		Y	Y	Y	Y	
ACQ-7 total score (de facto type estimand)	Y	Y		Y	Y	Y	Y	
E-RS total score using pooled FF doses (de facto type estimand)	Y	Y		Y	Y	Y	Y	
E-RS total score (de facto type estimand)	Y	Y		Y	Y	Y	Y	

